4.2.3. Sensitivity analyses

As a sensitivity analysis, a vague prior of Normal (-30, SD=50) will be applied instead of the robust MAP prior for placebo at Week 12.

4.2.4. Additional estimands

An additional estimand for the primary endpoint is defined: the intercurrent event of the use of Rescue Therapy will be handled with the treatment policy strategy: data collected after use of Rescue Therapy will be included in the statistical analysis.

Missing data assumption will be MAR, i.e., given the history of a subject, the part that is missing will be distributed similarly as those that are still in the study at that time, whether they have taken Rescue Therapy or not.

The same statistical approach as described in Section 4.2.2 will be used.

Primary endpoint additional analysis due to COVID-19

For the primary endpoint, if >= 6 participants in Group 1 have confirmed COVID-19 up to Week 12, then an additional analysis whereby the intercurrent event of the onset of COVID-19 (confirmed diagnosis only) will be handled with the hypothetical strategy may be conducted.

EASI scores collected after the onset of COVID-19 (confirmed diagnosis only) will be set to missing.

Missing observations will be assumed to be Missing at Random (MAR), i.e. assume that the missing part, given the history, will be like the data observed in the absence of COVID-19.

For the use of Rescue Thearpy, the same method (hypthetical stratgey) as in the primary analysis will be used.

4.3. Secondary Endpoints Analyses

For Safety analysis please refer to Section 4.5.

4.3.1. Clinical secondary endpoints

4.3.1.1. Definition of clinical endpoints

The secondary endpoints for Group 1 are:

- Change from baseline in the EASI at Week 12.
- EASI 50/75/90 responses at Week 12, EASI 50/75/90 response is defined as \geq 50/75/90% reduction in the EASI from Baseline.
- IGA score of 0 ('clear') or 1 ('almost clear') response at Week 12.

The secondary endpoint for Group 2 is:

• Percent change from baseline in the EASI at Week 12.

4.3.1.2. Main analytical approach

The analyses of the secondary endpoints will be based on the Safety analysis set. Participants will be analysed according to the treatment they received.

Group 1 – continuous endpoints

The approach is the same as that used for the primary endpoint (Section 4.2.2), including up to Week 12 visit. Vague prior of Normal(0, SD=10⁶) will be used for all parameters associated to the predictors. EASI scores will be set to missing after Rescue Therapy. Missing data will be assumed to be MAR.

Group 1 – binary endpoints

Bayesian logistic regression will be used.

Responses collected after use of Rescue Theapy will be set to non-responders.

Missing responses will be imputed as non-reponders.

Binary Endpoints					
 EASI50, EASI75, and EASI90 responses at Week 12 					
 IGA score of 0 or 1 	response at Week 12				
Analysis Method					
Bayesian Logistic Regi	ression				
Model Specification					
Outcome	$y_i = Ry_i = response (0/1)$ for participant i at Week 12				
Predictors	Treatment (categorical) Baseline score (continuous) Baseline score will be centered around its observed mean prior to inclusion in the model				
Model	$y_i \sim Ber(p_i)$ $logit(p_i) = (Treatment=Placebo) \times \beta_1 + (Treatment=GSK) \times \beta_2 + (Baseline\ score) \times \beta_3$				
Prior distributions for coefficients (β)	$\beta = \text{parameters associated to predictors}$ $\bullet \beta_1, \ \beta_2 \text{: vague prior such that logit}^{-1}(\beta_k) \sim \text{Beta}(1/3, \ 1/3)$ $\bullet \beta_3 \beta_k \text{: vague prior N}(0, \ \text{SD}=10^6)$				

Model Checking & Diagnostics

See Section 4.1.1

Results Presentation

- Adjusted posterior median and 95% Crl of true response rate for each treatment group, using the back-transformation of the logit (table).
- Posterior median and 95% Crl for the true difference in proportion of responders (GSK1070806

 placebo) (table)

- Probabilities that the true treatment difference is greater than 0 and 10%.
- Outputs will include results for earlier timepoints in addition to the objective specified timepoint
 of Week 12.

Group 2 - continuous endpoint

The PCFB in the EASI in Group 2 in the GSK1070806 arm will be analysed using a simplified version of the approach used for the primary endpoint (Section 4.2.2) with only one treatment arm. EASI scores will be set to missing after Rescue Therapy. Missing values are assumed to be Missing at Random (MAR). Vague priors of Normal(0, SD=10⁶) will be used for the parameters associated to the predictors.

4.3.1.3. Sensitivity analyses

No sensitivity analyses are planned for secondary efficacy endpoints.

4.3.1.4. Supplementary analyses

[figure not shown]
Data collected after use of Rescue Therapy may be used.

[figure not shown]
4.3.2. Immunogenicitiy

The immunogenicity analyses will be based on the Safety analysis set and will be reported for groups 1 and 2 combined.

[figure not shown]
The immunogenicity of GSK1070806 will be characterized with summary statistics of incidence, i.e. the number of participants with anti-drug antibodies by treatment over time. Immunogenicity testing involves a screening assay and a confirmation assay that together produce 3 results:

[figure not shown]
- Screening assay result (positive / negative)
- Confirmatory assay result (positive / negative) if positive result in the screening assay
- Titre result (numeric) if positive result in the confirmation assay.

[figure not shown]

[figure not shown]

CONFIDENTIAL

4.5. Safety Analyses

The safety analyses will be based on the Safety Analysis Set and reported for groups 1 and 2 combined. Participants will be analysed according to the treatment they received.

No formal statistical testing will be performed on Safety data.

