4. STUDY DESIGN

4.1. Overall Design

This is a multi-centre, 12-week, randomized, double-blind, parallel group, placebo-controlled study of GSK1070806 administered as a single 2 mg/kg IV and will investigate the efficacy and safety in moderate-severe AtD participants. See the Study Schematic (Section 1.2) and the Schedule of Activities (Section 1.3).

Study Populations and Randomisation

Group 1 - BN: for whom disease was not adequately controlled by topical treatments. Approximately 40 BN patients may need to be consented for screening to provide 30 randomized. Thirty BN participants will receive GSK1070806 or placebo in a 2:1 ratio (20 and 10 participants, respectively).

Group 2 - Dupi-IRs: patients whose disease was not adequately controlled following at least 16 weeks of dupilumab treatment (please refer to inclusion and exclusion criteria) or who could not tolerate dupilumab. Approximately 24 Dupi-IR patients may need to be consented for screening to provide 18 randomized. Eighteen Dupi-IR participants will receive GSK1070806 or placebo in a 5:1 ratio (15 and 3 participants, respectively).

Primary Efficacy Endpoint

The primary efficacy endpoint is percent change from baseline in the eczema area and severity index (PCFB EASI [Hanifin, 2001]) at Wk 12 in participants of Group 1.

Study Duration

Groups 1 and 2 will be conducted in parallel.

The overall study duration for an individual participant is not expected to exceed 28 weeks (Screening is 4 weeks; Treatment Period is 12 weeks; Follow-Up Period is 12 weeks).

The End of Study (Wk 24, Day 169) allows for continued safety monitoring beyond the Wk 12 primary endpoint in this new disease population (AtD), for which GSK1070806 has not yet been tested.

Treatment and Follow-Up Periods Screening Period

- The Screening Period is 28 days.
- All participants must stop using topical treatments (corticosteroids, calcineurin inhibitors or Phosphodiesterase 4 [PDEIV] inhibitors) for at least 7 days (starting on Day -7) prior to dosing on Day 1.
- Participants should apply bland topical emollient at least once from at least Day -7 (until at least Wk 12).
- Participants must record itch (PP-NRS) and fatigue (brief fatigue inventory, item 3) daily starting on Day -7 (see SoA Section 1.3).

Following the end of the single intravenous infusion of study treatment, participants are to be monitored for at least a two-hour period before discharge from the clinical unit.

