5. STUDY POPULATION

TMF-14679521

Inclusion Criteria Numbers 4 and 5 and Exclusion Criterion Number 21 distinguish the two study populations.

Prospective approval of protocol deviations to recruitment and enrolment criteria, also known as protocol waivers or exemptions, is not permitted.

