9.4.3. Secondary Endpoint(s)

9.4.3.1. Safety Endpoints

No formal statistical testing will be performed on safety data.

All safety evaluations will be based on the Safety analysis set and will be reported for group 1 and 2 together.

Clinical interpretation will be based upon review and displays of adverse events, laboratory values and vital signs. The principal consideration in this evaluation will be the

investigator-reported relationships of adverse events or the clinical important findings in laboratory tests to study treatment (refer to the SAP).

215253

The immunogenicity of GSK1070806 will be based on the PK analysis set and characterized with summary statistics of incidence, i.e. the number of participants with anti-drug antibodies by treatment over time.

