1.1. Objectives, Estimands and Endpoints

Objectives	Endpoints
Primary	
To compare the clinical effect of a single intravenous (IV) infusion of 2 mg/kg of GSK1070806 versus placebo in moderate to severe Atopic Dermatitis in the Biologic Naïve (BN) population (Group 1).	Percent change from baseline (PCFB) in the Eczema Area and Severity Index (EASI) at Week 12
Secondary	
• To further compare the clinical effect (GSK1070806 versus placebo) in the BN population (Group 1).	 Change from Baseline (CFB) in the EASI at Week 12. EASI 50/75/90 defined as ≥ 50/75/90% reduction in the EASI from Baseline at Week 12. Investigator Global Assessment (IGA) score of 0 or 1 at Week 12.
To estimate the clinical effect of GSK1070806 in the dupilumab inadequate responder (Dupi-IR) population (Group 2).	PCFB in the EASI at Week 12.
To assess safety and tolerability (GSK1070806 versus placebo) in the combined AtD population (Groups 1 and 2).	 Incidence of serious adverse events (SAEs) and adverse events (AEs). Incidence of clinically important findings in: Vital signs Electrocardiogram Laboratory: haematology, clinical chemistry and urinalysis.
To assess anti-drug antibody (ADA) formation in the combined AtD population (Groups 1 and 2).	Incidence of ADAs

Primary estimand

The primary clinical question of interest is: What is the treatment effect on Eczema Area and Severity Index (EASI) after 12 weeks of treatment with a single intravenous (IV) infusion of 2 mg/kg GSK1070806 versus placebo in Biologic Naïve participants (Group 1) with moderate to severe Atopic Dermatitis in the absence of use of Rescue Therapy.

[figure not shown]
The primary estimand is described by the following attributes:

- Population: Biologic Naïve (BN) participants with moderate to severe Atopic Dermatitis.
- Treatment condition: A single 2 mg/kg one-hour IV infusion of either GSK1070806 or placebo at Day 1.
- o Variable / endpoint: Percent change from Baseline to Week 12 in the EASI.
- o Summary measure: Difference (GSK1070806 placebo) in mean percent change from baseline in EASI at Week 12.
- o Intercurrent events: Use of Rescue Therapy. It will be handled with a hypothetical strategy, i.e. values after use of Rescue Therapy will be set to missing.

Rescue Therapy is defined in this document as the use of any prohibited medication (as defined in the protocol section 6.8.2) that is considered as an important protocol deviation.

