4.5.2. Adverse Events

Adverse event (AE) analyses including the analysis of AEs, Serious AEs (SAEs) and other significant AEs will be based on GSK Core Data Standards. Summary tables will include the number of participants with the AE, the percentage of participants with the AE. The definitions of AEs or SAEs will be detailed in OPS.

An AE is considered study intervention emergent if the AE onset date is on or after study intervention start date.

All AE summaries will be based on study intervention emergent events unless otherwise specified.

SAE summaries will be based on all SAEs reported regardless of whether they meet the definition of study intervention emergent or not.

All AE and SAE summaries will be presented by System Organ Class (SOC) & Preferred Term (PT) unless otherwise specified. Adverse events will be coded using the standard Medical Dictionary for Regulatory Affairs (MedDRA dictionary).

Summary tables will be produced for the following categories:

- 1. Adverse events by system organ class and preferred term and maximum intensity
- 2. Drug-related adverse events by system organ class and preferred term and maximum intensity
- 3. Serious adverse events by system organ class and preferred term (number of subjects and occurrences)
- 4. Common (>=0%) adverse events by overall frequency
- 5. Common (>=0%) non-serious adverse events by system organ class and preferred term (number of subjects and occurrences)
- 6. Serious adverse events by system organ class and preferred term and maximum intensity
- 7. Non-serious drug-related adverse events by overall frequency
- 8. Serious fatal and non-fatal drug-related adverse events by overall frequency

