4.6. Other Analyses

4.6.1. Subgroup analyses

There are no planned subgroup analyses for any of the endpoints.

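### Safety incidence is planned for both groups combined although allocation is 20:10 and 15:3; by-group columns in two tables would be a cheap, optional improvement

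*SAP*

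**What the plan says.** On reporting, SAP 4.5 reads: "The safety analyses will be based on the Safety Analysis Set and reported for groups 1 and 2 combined". Protocol 9.4.3.1 has the same rule: "All safety evaluations will be based on the Safety analysis set and will be reported for group 1 and 2 together". The safety objective in SAP 1.1 and Protocol 3 compares GSK1070806 with placebo in the combined population.

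On content, SAP 4.5.2 says: "Summary tables will include the number of participants with the AE, the percentage of participants with the AE". None of its eight listed AE and SAE tables names a split by group. SAP 4.6.1 adds: "There are no planned subgroup analyses for any of the endpoints". No formal testing of safety data is planned and no combined risk difference is described.

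On allocation, Protocol 4.1 says for Group 1: "Thirty BN participants will receive GSK1070806 or placebo in a 2:1 ratio", and for Group 2: "Eighteen Dupi-IR participants will receive GSK1070806 or placebo in a 5:1 ratio". On what separates the groups, Protocol 5 says: "Inclusion Criteria Numbers 4 and 5 and Exclusion Criterion Number 21 distinguish the two study populations". These criteria all concern prior treatment.

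**The concern.** The objective is a comparison with placebo, so readers will set the two pooled percentages side by side. Because the ratios differ, the pooled arms contain different proportions of Dupi-IR participants. This follows from the design and is not a chance imbalance. If Dupi-IR participants have a different background event rate from biologic-naïve ones, part of any difference between the pooled percentages reflects group mix and not the drug. A combined table alone does not let the reader see this.

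Whole-number example with no drug effect: 2/20 v 1/10 in Group 1 (10% in both arms) and 5/15 v 1/3 in Group 2 (33.3% in both arms) pool to 7/35 = 20.0% v 2/13 = 15.4%.

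At stake is how a descriptive table is read. No test or stated decision rule depends on it.

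**Working it through.** **Inputs.** Arm sizes come from Protocol 4.1 and SAP 5. Event rates by group appear in neither document, so p1 (Group 1) and p2 (Group 2) below are assumptions, and q = 1 − p.

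**1. The plan's own figures.** 30 × 2/3 = 20 and 30 × 1/3 = 10; 18 × 5/6 = 15 and 18 × 1/6 = 3; total 48. These agree with the documents. The pooled arms are 35 GSK1070806 and 13 placebo.

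**2. Group 2 share of each pooled arm.** 15/35 = 0.4286 and 3/13 = 0.2308; difference 0.1978.

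**3. Expected pooled difference with no drug effect.**

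(20·p1 + 15·p2)/35 − (10·p1 + 3·p2)/13 = 0.1978 × (p2 − p1)

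For example, p1 = 0.3 and p2 = 0.5 give 13.5/35 = 38.6% v 4.5/13 = 34.6%, a difference of 4.0 points. If Group 1 has the higher rate the sign reverses.

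**4. Comparison with sampling error.**

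SE = sqrt[(20·p1·q1 + 15·p2·q2)/35² + (10·p1·q1 + 3·p2·q2)/13²]

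| Assumed p1, p2 | Shift (points) | SE (points) | Shift/SE |
|---|---|---|---|
| 40%, 40% | 0 | 15.9 | 0 |
| 40%, 50% | 2.0 | 16.0 | 0.12 |
| 30%, 50% | 4.0 | 15.3 | 0.26 |
| 40%, 70% | 5.9 | 15.6 | 0.38 |
| 30%, 70% | 7.9 | 14.9 | 0.53 |
| 5%, 10% | 1.0 | 7.9 | 0.12 |
| 5%, 20% | 3.0 | 9.2 | 0.32 |

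The last two rows are nearer to what a single preferred term might show. One placebo event moves the pooled placebo column by 1/13 = 7.7 points.

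**5. Dependence on enrolment.** The factor 0.198 assumes full planned enrolment. Sizes are approximate, and Group 2 recruitment may stop at an interim analysis (Protocol 4.1 and 9.5.2). With Group 1 complete and Group 2 stopped in ratio:

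- at 12 participants (10:2): 10/30 − 2/12 = 0.167, or 1.7 points per 10-point gap;
- at 6 participants (5:1): 5/25 − 1/11 = 0.109, or 1.1 points per 10-point gap.

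**6. What by-group columns can show.** The denominators would be 20, 10, 15 and 3. The Group 1 contrast (20 v 10) is free of the mix. The Group 2 contrast is not usable alone: one placebo event is 1/3 = 33 points, and its SE, sqrt[p·q·(1/15 + 1/3)], is 29 points at p = 0.3 or 0.7 and 32 points at p = 0.5. Nor can the columns test for a rate gap. At 30% v 50% the gap is 0.20/sqrt(0.21/20 + 0.25/15) = 0.20/0.165 = 1.2 SE among GSK1070806 participants, and 0.20/sqrt(0.21/10 + 0.25/3) = 0.20/0.323 = 0.6 SE among placebo participants.

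**The case against.** The strongest reply is that this is a preference about display. Objective, protocol and SAP agree on combined reporting. Protocol 4.2 separates the groups for clinical endpoints because of a putative difference in efficacy, and no passage suggests a difference in background safety. Safety is descriptive, and Protocol 9.4.3.1 makes investigator-reported relationship the principal consideration. Every non-zero shift needs an assumed gap and stays within sampling error. The added Group 2 placebo column holds 3 participants, in an arm that Protocol 4.2 says exists to maintain the blind. All of this stands, and it limits the point to an optional improvement. It does not remove the point, because the difference in mix is certain at the planned sizes and the Group 1 columns give a contrast free of it.

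Three stronger readings may tempt a reader and are not supported:

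- *The pooled safety comparison is wrong or biased.* It is shifted only if background rates differ, and the documents give none. Inclusion criterion 5b admits participants intolerant to dupilumab owing to adverse events, which is a reason not to presume equal rates but is not evidence of a gap.
- *No by-group safety display will exist.* The SAP text points that way, but the Output and Programming Specification, to which the SAP defers some display detail, is not available. SAP 4.6.1 settles little, since the two groups are separately randomised populations and not clearly subgroups.
- *The safety comparison needs a stratified estimate, or every safety table needs splitting.* No combined risk difference is planned, so there is nothing to stratify. Splitting all laboratory, vital-sign and QTcF shift tables would add four columns to many displays for little return.

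**Conclusion.** The point holds as a low-severity improvement to a display. At full planned enrolment the pooled arms differ by 19.8 points in their share of Group 2. With no drug effect this produces about 2.0 points of difference per 10-point gap in background rate, or 1.7 or 1.1 points if Group 2 stops at 12 or 6 participants. Over assumed gaps of 0 to 40 points the shift is 0 to 7.9 points, at most 0.53 SE. The conclusion rests on the planned arm sizes, on assumed rates and on the SAP text alone. The case for acting is the low cost, not the size of the effect.

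**What to change.** In SAP 4.5, keep the combined columns that the objective and Protocol 9.4.3.1 require. Unless the Output and Programming Specification already does so, add treatment-within-group counts and percentages to two tables in the SAP 4.5.2 list: the fourth (common AEs by overall frequency) and the third (SAEs by system organ class and preferred term). Use the actual group from the CRF, as SAP 4.1 already defines it. Add a footnote that the Group 2 contrast, with 3 placebo participants, is not to be interpreted alone.

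Record the addition in SAP 4.8 before unblinding, which means before the first unblinded interim analysis if one is held. The choice then cannot be seen as a response to an observed imbalance.

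Cost: a few lines of SAP text and four extra columns in each of two tables, with no new data. No protocol amendment is needed, because combined reporting is still delivered and Protocol 9.4 leaves technical detail to the SAP. The downsides are wider tables and a sparse Group 2 placebo column.

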4.5.1. Extent of Exposure

A listing of exposure to study treatment will be produced.

4.5.2. Adverse Events

Adverse event (AE) analyses including the analysis of AEs, Serious AEs (SAEs) and other significant AEs will be based on GSK Core Data Standards. Summary tables will include the number of participants with the AE, the percentage of participants with the AE. The definitions of AEs or SAEs will be detailed in OPS.

An AE is considered study intervention emergent if the AE onset date is on or after study intervention start date.

All AE summaries will be based on study intervention emergent events unless otherwise specified.

SAE summaries will be based on all SAEs reported regardless of whether they meet the definition of study intervention emergent or not.

All AE and SAE summaries will be presented by System Organ Class (SOC) & Preferred Term (PT) unless otherwise specified. Adverse events will be coded using the standard Medical Dictionary for Regulatory Affairs (MedDRA dictionary).

Summary tables will be produced for the following categories:

- 1. Adverse events by system organ class and preferred term and maximum intensity
- 2. Drug-related adverse events by system organ class and preferred term and maximum intensity
- 3. Serious adverse events by system organ class and preferred term (number of subjects and occurrences)
- 4. Common (>=0%) adverse events by overall frequency
- 5. Common (>=0%) non-serious adverse events by system organ class and preferred term (number of subjects and occurrences)
- 6. Serious adverse events by system organ class and preferred term and maximum intensity
- 7. Non-serious drug-related adverse events by overall frequency
- 8. Serious fatal and non-fatal drug-related adverse events by overall frequency

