1.2. Schema

1.3. Schedule of Activities (SoA)

1.3.1. Screening Period

| PROCEDURE | SCREENING PERIOD Up to Day -28 | NOTES: Please also refer to Appendix 2. Screening may be performed across one or more visits if needed. |
|---|-----------------------------------|---|
| Informed Consent | X | |
| Inclusion/Exclusion Criteria | X | |
| Demography | X | |
| Physical Examination (Full) | X | |
| Height and Weight | X | |
| Medical/medication/drug/alcohol history | X | |
| Alcohol Screen | X | As per standard local practice. |
| Urine Drug Screen | X | |
| HIV, Hepatitis B and C. | X | |
| COVID-19 (SARS-CoV-2) Test | х | EITHER a documented (Regulatory Approved) negative test within two days of Initial Screen OR test performed at Initial Screen |
| TB Screening (QuantiFERON) | X | |
| Pregnancy Test (serum, WOCBP) or FSH/Oestradiol (serum, WONCBP) | х | WOCBP must have confirmed menstruation within 28 days of anticipated dosing on Day 1 and continue to return a negative pregnancy test up to and including prior to dosing on Day 1. |
| 12-lead ECG | Triplicate | |
| Vital Signs | X | |
| Haematology, Clinical Chemistry | X | See Appendix 2. |
| Urinalysis | X | See Appendix 2. |
| Clinical Assessments (Screening EASI, IGA) | X | Inc Criterium No. 1 |
| Identify target lesion | X | |
| STOP TCS /TCI /topical PDEIVi | Day -7 onwards | Inc. Crit. No. 9 - Participant must STOP Topicals at Day -7 |
| START application of bland emollient | Day -7 onwards | |
| PP-NRS (itch) | Day -7 onwards | Record daily |
| | Day -7 onwards | Record daily |
| SAE assessment | X | From signing the Informed Consent Form |

TMF-14679521 **CONFIDENTIAL** 215253

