| Randomization & DOSING (IV inf.) | X | | | | | | | | | | | |
| Skin Biopsy (Lesion and Non-Lesional) | (X) ¹ | | | X | | X | | | | | 1) Non-Lesional Biopsy obtained only on Day 1. RNAseq and IHC (Section 8.7.4) | |
| Skin Tapestripping | (X) | | | Х | | X | | | | | RNAseq and Proteomics (Section 8.7.5) | |
| Pharmacokinetics (PK) | (X) ¹ | х | х | х | х | Х | Х | Х | Х | Х | 1) Day 1 PK samples: prior to infusion, immediately at the end of infusion and then 2 | |
| Target Engagement (TE) | (X) | х | Х | х | х | Х | Х | Х | Х | Х | hours post - end of infusion. TE assessment is comprised of at least, but not limited to, Total IL-18. (Section 8.7.1.) | |
| Serum Biomarkers (incl proteomics) | (X) | | | X | | Х | | X | X | X 1 | | |
| Whole Blood: RNA Sequencing | (X) | | | X | | X | | | | ^ | PAX gene tubes - (Section 8.7.3.) | |
| mmunogenicity | (X) | | | X | Х | Х | | X | X | Х | (Section 8.8.) | |
| PGx | X | | | | | | | | | | PGx is optional (Section 8.6.) | |
| SAE and AE | <> | | | | > | X | Х | SAEs recorded throughout. AEs recorded from start of IV infusion. | | | | |
| Concomitant Medications <> X X | | | | | | | | | | | | |
| Note: On Day 1, all activities and blood s | ample | es ar | e to | be a | cqui | ired p | rior to | dosing , | unle | ss sta | ted otherwise. | |
| Note: (X) brackets denote the Baseline A | ssessi | men | t. | | | | | | | | | |

TMF-14679521 215253

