8.4.1. Time Period and Frequency for Collecting AE and SAE Information

- All SAEs will be collected from the signing of the informed consent form (ICF) until the follow-up visit at the time points specified in the SoA (Section 1.3).
- All AEs will be collected from the start of study intervention until the follow-up visit at the time points specified in the SoA (Section 1.3).
- Medical occurrences that begin before the start of study intervention but after obtaining informed consent will be recorded as Medical History/Current Medical Conditions not as AEs.
- All SAEs will be recorded and reported to the sponsor or designee immediately and under no circumstance should this exceed 24 hours, as indicated in Appendix 3. The investigator will submit any updated SAE data to the sponsor within 24 hours of it being available.
- Investigators are not obligated to actively seek information on AEs or SAEs after the conclusion of the study participation. However, if the investigator learns of any SAE, including a death, at any time after a participant has been discharged from the study, and he/she considers the event to be reasonably related to the study intervention or study participation, the investigator must promptly notify the sponsor.

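### The by-treatment SAE tables include SAEs that began before the infusion, which adds noise to the descriptive GSK1070806-versus-placebo SAE incidence and dilutes it

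*SAP*

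**What the plan says.** SAP 4.5.2 sets two counting rules side by side. For AEs: "All AE summaries will be based on study intervention emergent events unless otherwise specified". For SAEs: "SAE summaries will be based on all SAEs reported regardless of whether they meet the definition of study intervention emergent or not". Emergence is decided by calendar date: "An AE is considered study intervention emergent if the AE onset date is on or after study intervention start date".

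The collection windows differ in the same way. Protocol 8.4.1 says "All SAEs will be collected from the signing of the informed consent form (ICF) until the follow-up visit", and the screening schedule (Protocol 1.3.1) starts SAE assessment "From signing the Informed Consent Form". The treatment schedule (Protocol 1.3.2) notes: "SAEs recorded throughout. AEs recorded from start of IV infusion". Protocol 8.4.1 also says that medical occurrences between consent and the start of study intervention "will be recorded as Medical History/Current Medical Conditions not as AEs".

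The safety tables use the Safety analysis set (randomized and dosed participants), with both groups combined and participants shown under the treatment they received (SAP sections 3 and 4.5). SAE incidence is an endpoint of a secondary objective that compares GSK1070806 with placebo (SAP 1.1). SAP 6.2.2 defines a pre-intervention period, but no SAE table listed in 4.5.2 is split by it and no emergent-only SAE table is listed.

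**The concern.** A participant can have an SAE during screening, recover, be found eligible and be dosed. Under the SAP rule that SAE counts towards the SAE incidence of the arm later assigned, although no study treatment had been given when it began. It carries no information on the treatment comparison that the endpoint is meant to describe.

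The SAP applies this reasoning to AEs and drops it for the rarer and weightier events. As a result, an SAE can stand in table 3 or 6 (SAEs by system organ class and preferred term) and be missing from table 1 (all AEs), so the SAEs shown need not be a subset of the AEs shown. With 13 placebo participants, one such event is visible in the display.

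**Working it through.** The plan states no figure that depends on this rule, so there is nothing to reproduce. The check traces the rule and then gives its scale.

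**Which tables are affected**

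| Step | Source | Result |
|---|---|---|
| SAE collection starts | Protocol 8.4.1, 1.3.1 | Consent, up to 28 days before Day 1 |
| Who enters the tables | SAP 3, 4.5 | Dosed participants only, by treatment received |
| Which SAEs count | SAP 4.5.2 | All, emergent or not |
| Which AEs count | SAP 4.5.2 | Emergent only |
| Randomization | Protocol 1.3.2 | Day 1, in the same row as dosing |

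The rule therefore reaches SAEs with onset between consent and infusion in participants who are later dosed. Tables 3 and 6 take them in. Table 8 is limited to drug-related SAEs, and an event before any exposure should not qualify.

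**Denominators** (SAP 1.2)

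- GSK1070806: 20 + 15 = 35
- Placebo: 10 + 3 = 13
- Total: 35 + 13 = 48

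**Effect of one participant with a pre-infusion SAE and no emergent SAE**

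- GSK1070806: 1/35 = 2.9 percentage points
- Placebo: 1/13 = 7.7 percentage points

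**Share of the window before treatment**

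Screening is up to 4 weeks, and treatment plus follow-up is 24 weeks: 4/(4 + 24) = 14.3%. This is the maximum share of time, not a share of events.

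**Chance that it happens**

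The documents give no SAE rate. Assume a 24-week SAE risk r between 1% and 10%, a constant hazard, and a full 4-week screening period. The 4-week risk is p = 1 − (1 − r)^(4/24), and the chance of at least one affected participant among n is 1 − (1 − p)^n. For r = 5%, p = 1 − 0.95^(1/6) = 0.0085. For n = 48 this gives 1 − 0.95^8 = 33.7%.

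| Assumed r | p over 4 weeks | At least one among 48 | At least one among 13 placebo |
|---|---|---|---|
| 1% | 0.17% | 7.7% | 2.2% |
| 3% | 0.51% | 21.6% | 6.4% |
| 5% | 0.85% | 33.7% | 10.5% |
| 10% | 1.74% | 57.0% | 20.4% |

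These are probably upper bounds. Screening can be shorter than 28 days, and the exclusion criteria and the Day 1 re-check remove some participants who had a screening SAE.

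**Dilution**

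Take a placebo risk of 5% over 24 weeks and a true hazard ratio of 2 after dosing, with the placebo hazard in both arms during screening.

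- Emergent SAEs only: active 1 − 0.95^2 = 9.75%, placebo 5%. Ratio 9.75/5 = 1.95, difference 4.75 points.
- All SAEs: active 1 − 0.95^(2 + 1/6) = 10.52%, placebo 1 − 0.95^(28/24) = 5.81%. Ratio 10.52/5.81 = 1.81, difference 4.71 points.

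The expected ratio moves towards 1, while the expected difference hardly changes.

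**The case against.** The strongest reply is that the rule is stated openly, keeps every SAE in a dosed participant visible (including any from screening procedures or the topical washout), and does little harm. Much of this stands.

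- **Balance.** Almost all pre-infusion SAEs precede Day 1 randomization, so they cannot depend on the arm. A reader might infer a bias for or against GSK1070806; the design does not support that.
- **Scope.** A reader might infer that every SAE from consent enters the tables. It does not: screen failures and participants never dosed are outside the Safety set. The exclusions for recent infection, hospitalization for infection and major surgery narrow it further.
- **Causality.** A reader might infer that the tables attribute these events to the drug. Standing in an arm's column is not a causal judgement, and Protocol 9.4.3.1 rests interpretation mainly on the investigator's view of relationship and on clinically important laboratory findings.
- **Inference.** No hypothesis is tested and no formal safety testing is planned.
- **Traceability.** The two windows appear in adjacent sentences, and onset dates identify the events in a 48-participant trial. To call the AE and SAE tables irreconcilable would go too far.
- **Unseen rules.** SAP 4.5.2 leaves the AE and SAE definitions to the output and programming specification, which is not among the documents.

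What the reply does not answer is that the listed SAE tables offer no emergent-only view. Balance in expectation is weak comfort with 13 placebo participants, and the descriptive display is the planned comparison of SAE incidence. Full disclosure does not require mixing the two periods, because a separate display preserves it.

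**Conclusion.** The point holds as a presentation problem in a secondary safety endpoint. SAP 4.5.2 counts SAEs that began before the infusion in the by-arm tables, chiefly tables 3 and 6, while the AE tables leave out events before the start date. The consequence is chance noise and some dilution, not directional bias and not an effect on any test.

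The size per affected participant, 2.9 points on GSK1070806 or 7.7 on placebo, follows from the planned numbers and assumes no emergent SAE in the same participant. How often it would occur cannot be derived from the documents. The range of 7.7% to 57.0% rests on the assumed SAE risks, a constant hazard and a full screening period. The fall in the ratio from 1.95 to 1.81 rests in addition on the assumed hazard ratio of 2.

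One uncertainty remains in the protocol. Section 8.4.1 collects SAEs from consent but records pre-dose medical occurrences as history, and does not say which rule governs a pre-dose SAE. The number of such events that would reach the SAE dataset is therefore unclear, which is a further reason for an explicit rule.

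**What to change.** In SAP 4.5.2:

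1. Base the by-arm SAE incidence in tables 3 and 6 on study-intervention-emergent SAEs. Alternatively, keep the all-SAE tables and add an emergent-only version beside them.
2. List SAEs with onset before the infusion separately, so that nothing is lost from disclosure.
3. State how Day 1 is handled. The emergent definition works by date, so a Day 1 SAE before the infusion (for example after the pre-dose biopsy) would still count as emergent. Use onset time relative to the start of infusion where it is collected. Where it is not, SAP 6.2.2 already treats the first dose date as on-intervention for AEs.
4. Reconcile with Protocol 8.4.1 whether a pre-dose SAE is recorded as an SAE or as medical history, and say so in both documents.

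The cost is about one SAP sentence and one extra display or listing, plus a clarification of 8.4.1. No new data are needed if onset time is already collected, and SAE collection and reporting to the sponsor do not change.
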